9.7 Handling of Missing Data

Missing data will not be imputed.

Per the published scoring guidelines for the ASQ, the overall score is calculated by taking the average of the non-missing items.

All analyses will be described in the study Statistical Analysis Plan, which will supersede the methodology presented in the Study Protocol. Any deviations in the Statistical Analysis Plan will be recorded along with their rationale in the final study report, as appropriate.

10 ADVERSE EVENT REPORTING

10.1 Definition of Adverse Events

An adverse event (AE) is any unfavorable or unintended sign, symptom, or disease temporally associated with the use of an investigational product or protocol-imposed intervention, regardless of attribution. All observed or volunteered adverse events regardless of suspected causal relationship to the investigational product(s) will be reported as described in the following sections.

Potential side effects from routine nasal swabbing, including, but not limited to, acute epistaxis (nosebleed), sneezing, nasal redness, are not required to be reported to the Sponsor as adverse events.

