10.2 Reporting Period

Adverse events collection begins at enrollment and ends after completion of the sample collection. Adverse events will only be recorded for events that occur during or are believed to be associated with the nasal swab sample collection procedures. All AEs will be reported on the adverse event page(s) of the CRF.

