13 ETHICS

13.1 Risk Analysis

13.1.1 Risk to the subject

CONFIDENTIAL

May not be reproduced nor disseminated outside of Exact Sciences without permission

The risk to study subjects is minimal and are related to the use of the nasal swab collection materials. The nasal swab could cause mild discomfort or a short-term impact such as a nosebleed. While the saline in the collection tube could spill, the liquid is safe and of small volume.

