**Listing 34. Listing of Adverse Events, Serious Adverse Events, and Deviations (if any are reported)**

Subject ID	Critical Task ('Yes'; otherwise NP*)	Age Group (<18, 18-30, 31-45, 46-65, >65)	Education (No HS, some HS, HS, college, advanced)	Test Result	Description of Adverse Event, Serious Adverse Event, and any deviations (or "None Reported")
01	NP				
02	NP				
03	NP				
...					

\* NP = Task not pre-specified as critical.

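### Protocol 10.1 makes reporting of swabbing side effects such as nosebleed optional while 10.2 and SAP 7.2.6.1 carry no such exemption, so an empty Listing 34 cannot be read as no swab-related harm

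*Protocol*

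**What the plan says.** Protocol 10.1 defines an AE broadly, as "any unfavorable or unintended sign, symptom, or disease temporally associated with the use of an investigational product or protocol-imposed intervention, regardless of attribution". It continues: "All observed or volunteered adverse events regardless of suspected causal relationship to the investigational product(s) will be reported as described in the following sections". Its next paragraph carves out a class of events from what must reach the sponsor: "Potential side effects from routine nasal swabbing, including, but not limited to, acute epistaxis (nosebleed), sneezing, nasal redness, are not required to be reported". The list is open-ended, and the paragraph sets no limit of severity or duration.

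Protocol 10.2 narrows the scope ("Adverse events will only be recorded for events that occur during or are believed to be associated with the nasal swab sample collection procedures") and then states, without exception, "All AEs will be reported on the adverse event page(s) of the CRF". Protocol 10.3 sends any SAE to the IRB and makes no exception for swabbing effects.

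Protocol 13.1.1 describes the risk to subjects: "The nasal swab could cause mild discomfort or a short-term impact such as a nosebleed". Its only other item is a saline spill, which it describes as safe.

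In the SAP, item 7.2.6.1 is a yes/no question in which the observer states whether the subject had or reported any AE. It does not repeat the exemption. Listing 34 has one row per subject and a free-text column headed "Description of Adverse Event, Serious Adverse Event, and any deviations (or 'None Reported"; it has no note on exempt events.

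**The concern.** A nosebleed after swabbing meets the protocol's own definition of an AE. One sentence of 10.1 says it will be reported, and the next paragraph says it need not be. Two observers who see the same nosebleed could answer SAP 7.2.6.1 differently, and each could cite the protocol.

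The exempt events are not incidental. They are the bodily effects that the risk section itself attributes to the swab. SAP section 2 says the clinical study report will be attached to an FDA filing for home self-collection, and SAP section 3 describes that setting as one without supervision by a healthcare worker. A reader of that report would naturally take a column of None Reported entries to mean that about 30 people used the swab without harm. The plan does not guarantee the data that would support this reading.

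**Working it through.** The point rests on the text. The plan states no safety figure, so there is nothing to reproduce.

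**Step 1: the rules applied to one event, a nosebleed during swabbing.**

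| Source | What it implies |
|---|---|
| Protocol 10.1, definition | It is an AE: an unintended sign, temporally associated, attribution irrelevant |
| Protocol 10.1, general rule | Report it |
| Protocol 10.1, exemption | Need not be reported to the sponsor as an AE; nosebleed is named |
| Protocol 10.2, scope | Within scope: it occurs during collection |
| Protocol 10.2, CRF rule | Enter it on the AE page |
| Protocol 10.3 | To the IRB only if serious |
| SAP 7.2.6.1 | Answer yes, if the question is taken at face value |
| SAP Listing 34 | Shown if reported; otherwise None Reported |

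A blank AE page and a completed one are both consistent with some part of the plan.

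**Step 2: the exemption against the named risks.** Protocol 13.1.1 names two bodily effects of the swab. Nosebleed is exempt by name. Discomfort is not listed, but the exemption's list is expressly not exhaustive, so it fits there. The saline spill is not a side effect of swabbing and is not clearly exempt.

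**Step 3: what an empty listing can mean.** It is compatible with (a) no swabbing effect occurred, or (b) one or more occurred and were left off as permitted. Nothing in Listing 34 separates the two.

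**Step 4: illustration of how likely (b) could be.** Inputs: N = 30 (target enrolment, Protocol 9.1) and an assumed per-subject rate p of any exempt event. The documents give no p, so a range is shown. The formula is P(at least one event) = 1 − (1 − p)^30.

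- p = 1%: 1 − 0.99^30 = 0.260, or 26%
- p = 2%: 1 − 0.98^30 = 0.455, or 45% (0.4545 before rounding)
- p = 5%: 1 − 0.95^30 = 0.785, or 79%
- p = 10%: 1 − 0.90^30 = 0.958, or 96%

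**Step 5: what complete capture would allow.** If every event were recorded and none occurred in 30 subjects, the upper 95% bound on the rate would be 1 − 0.05^(1/30) = 9.5% one-sided, or 1 − 0.025^(1/30) = 11.6% two-sided exact. When recording is optional, zero entries are not zero events, and neither bound can be stated.

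**The case against.** The case for leaving the text alone is that this is a one-day, minimal-risk usability study with no safety objective or endpoint, and that SAP 8.6 makes all analyses descriptive. Exempting minor expected effects is a disclosed choice, and the study report will describe the methods. The link to the Observer Form is redacted and the AE page is not shown, so the wording put to the observer cannot be checked. All of this is fair. It keeps the point at the level of a cheap improvement, but it does not resolve the conflict within the visible text.

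Five stronger readings are tempting, and the documents do not support them.

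- **That these harms cannot appear in Listing 34.** The exemption says reporting is not required; it does not forbid it. Protocol 10.2 and SAP 7.2.6.1, read alone, would bring a nosebleed in.
- **That serious harm could be hidden.** The exemption has no severity limit of its own, but 10.3 still sends SAEs to the IRB without a carve-out, and Listing 34 prints them.
- **That almost every event is removed.** Section 10.2 also covers events during collection that are not swabbing effects, such as an unrelated faint. In 10.1 the word routine qualifies the swabbing, so bleeding after the swab is pushed further than the instructions say may arguably fall outside the exemption.
- **That the root-cause review loses its signal.** That review draws on free text (SAP 7.5.2.4 and 8.2.4). Tasks 2.9 and 2.10 are graded critical tasks with observer feedback in Listings 12 and 13, and subjects are asked which steps gave trouble. A bleed may be noted there. However, no field asks for it, and the use errors for swabbing the nose in Protocol Table 2 concern too little swabbing, not too much force.
- **That the probabilities measure a defect.** They illustrate assumed rates, and the plan never set out to state a bound on harm.

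**Conclusion.** The point holds in a limited form. Protocol 10.1 conflicts with its own preceding sentence and with 10.2, and SAP 7.2.6.1 does not settle the matter. The swab harms named in 13.1.1 need not appear in Listing 34, and their capture depends on which rule the observer applies. A listing that reads None Reported is therefore not evidence of no swab-related harm.

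The consequence is confined to the safety statement; the primary endpoint and the usability analyses do not depend on it. Its numerical size is unknown because the documents give no event rate. The 26% to 96% range for at least one event in 30 depends entirely on the assumed rates of 1% to 10%. The conclusion also assumes that the forms not shown do not already settle what the observer should record.

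**What to change.** Reconcile Protocol 10.1 with 10.2 and SAP 7.2.6.1. The preferred change is to have observed or volunteered swabbing effects (nosebleed, sneezing, redness, discomfort) recorded on the existing AE page of the CRF, flagged as expected and needing no separate notification. Show them in Listing 34, and add a count and percentage of enrolled subjects with any such event. Because Listing 34 is a by-subject listing, the count needs an added summary line.

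If the sponsor keeps the exemption, state in 10.2 and SAP 7.2.6.1 that it applies, and footnote Listing 34 with the exempt events so that None Reported is not over-read.

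The cost is a short protocol amendment, which needs IRB approval under Protocol 13.2, a small SAP edit, and a few more minor CRF entries. The observer is already watching each of about 30 subjects and already answers the AE question.

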10.2 Reporting Period

Adverse events collection begins at enrollment and ends after completion of the sample collection. Adverse events will only be recorded for events that occur during or are believed to be associated with the nasal swab sample collection procedures. All AEs will be reported on the adverse event page(s) of the CRF.

10.3 Serious Adverse Events

Serious adverse events are not expected for this study. In the event of an SAE, the event will be reported to the IRB per IRB standard operating procedure.

11 QUALITY CONTROL AND QUALITY ASSURANCE

The study site may be subject to review by the (IRB)/Ethics Committee (EC), and/or to quality assurance audits performed by Exact Sciences.

CONFIDENTIAL

May not be reproduced nor disseminated outside of Exact Sciences without permission

12 DATA HANDLING AND RECORD KEEPING

All references to the Sponsor in this section include all designees e.g., Contract Research Organizations or Consultants acting on behalf of the Sponsor.

12.1 Protocol Deviations

The site should make all efforts not to deviate from any of the study procedures or requirements as described in this protocol, except where necessary to eliminate immediate risks to the subject(s).

Any deviations from this protocol must be notified to the Sponsor and documented properly. Protocol deviations must also be reported to the IRB per IRB policy.

12.2 Case Report Forms (CRFs)

As used in this protocol, the term Case Report Form (CRF) should be understood to refer to either a paper form or an electronic data record or both, depending on the data collection method used in this study.

A CRF is required and should be completed for each enrolled subject. The completed original CRFs are the sole property of Exact Sciences and should not be made available in any form to third parties, except for authorized representatives of Exact Sciences or appropriate regulatory authorities, without written permission from Exact Sciences.

12.3 Records Retention

The ICH E6(R2) Good Clinical Practice: Consolidated Guidance defines source documents as, "Original documents, data, and records (e.g., hospital records, clinical and office charts, laboratory notes, memoranda, subjects' diaries or evaluation checklists, pharmacy dispensing records, recorded data from automated instruments, copies or transcriptions certified after verification as being accurate copies, microfiches, photographic negatives, microfilm or magnetic media, x-rays, subject files, and records kept at the pharmacy, at the laboratories and at medico-technical departments involved in the clinical trial)."

The Sponsor agrees to keep records, including the identity of all participating subjects, all original signed informed consent forms, copies of all CRFs, and adequate documentation of relevant correspondence (e.g., letters, meeting minutes, telephone calls reports). The Sponsor shall maintain study records for a period of 2 years after the latter of the following three dates: the date on which the investigation is terminated or completed, the date that the records are no longer required for purposes of supporting a premarket approval application or a notice of completion of a product development protocol, or date provided in applicable national law.

13 ETHICS

13.1 Risk Analysis

13.1.1 Risk to the subject

CONFIDENTIAL

May not be reproduced nor disseminated outside of Exact Sciences without permission

The risk to study subjects is minimal and are related to the use of the nasal swab collection materials. The nasal swab could cause mild discomfort or a short-term impact such as a nosebleed. While the saline in the collection tube could spill, the liquid is safe and of small volume.

13.1.2 Benefit to Subject

There are no benefits to the subjects enrolled in this study.

13.2 Institutional Review Board (IRB) / Ethics Committee (EC)

It is the responsibility of the Investigator to have prospective approval of the study protocol, protocol amendments, informed consent forms, and other relevant documents, e.g., recruitment advertisements, if applicable, from the IRB. All correspondence with the IRB/EC should be retained in the Investigator File. Copies of IRB approvals should be forwarded to Exact Sciences or designee.

13.3 Ethical Conduct of the Study

The study will be conducted in accordance with legal and regulatory requirements, as well as the general principles set forth in the International Ethical Guidelines for Biomedical Research Involving Human Subjects (Council for International Organizations of Medical Sciences 2002), the Declaration of Helsinki (World Medical Association), and applicable local regulatory requirements and laws.

13.4 Subject Information and Consent

All parties will ensure protection of subject personal data and will not include subject names on any Sponsor forms, reports, publications, or in any other disclosures, except where required by laws. In case of data transfer, Exact Sciences will maintain high standards of confidentiality and protection of subject personal data. Subject name, contact information, and informed consent will be retained by Exact Sciences Clinical Affairs in a secure, limited access location, for the purpose of conducting and oversight of the clinical study. Subject protected health information, including name and date of birth, may be shared on a limited basis with Exact Sciences staff responsible for conducting data collection and analysis activities.

The informed consent form must be in compliance with ICH GCP, local regulatory requirements, and legal requirements. The informed consent form used in this study, and any changes made during the study, must be prospectively approved by both the IRB/EC and Exact Sciences before use.

The Investigator must ensure that each study subject, or his/her legally acceptable representative, is fully informed about the nature and objectives of the study and possible risks associated with participation. The Investigator, or a person designated by the Investigator, will obtain written informed consent from each subject or the subject's legally acceptable representative before any study-specific activity is performed. The Investigator will retain the original of each subject's signed consent form.

14 DEFINITION OF END STUDY

End of Study is defined when the enrollment target of approximately 30 subjects has been achieved and all samples have been collected, processed, and tested.

15 SPONSOR DISCONTINUATION CRITERIA

CONFIDENTIAL

May not be reproduced nor disseminated outside of Exact Sciences without permission

Premature termination of this study may occur because of a regulatory authority decision, change in opinion of the IRB, or at the discretion of Exact Sciences.

APPENDIX 1.0 – SCHEDULE OF ACTIVITIES

Activity	Observed Sample Collection
Informed Consent ¹	X
Subject Completed Demographics and Exclusion Criteria	X
Use of SARS-CoV-2 Specimen Collection Materials while under observation	X
Complete the After-Scenario Questionnaire (ASQ)	X
Answer observer questions about comprehension of IFU and observations	X

Footnotes for Schedule of Activities

1. Informed Consent must occur prior to undergoing any study specific procedures

CONFIDENTIAL

May not be reproduced nor disseminated outside of Exact Sciences without permission

APPENDIX 2.0 – IFU FROM SARS-CoV-2 TEST SPECIMEN COLLECTION MATERIALS

IFU from the SARS-CoV-2 Test Specimen Collection Materials are provided as a supplement to the clinical study protocol.

CONFIDENTIAL

May not be reproduced nor disseminated outside of Exact Sciences without permission

APPENDIX 3.0 – FORMS FOR DATA TO BE COLLECTED

Subject Demographics

- Education level
 - No high school
 - Some high school
 - High school
 - College degree
 - Advanced degree
- Date of birth
- Race/ethnicity
- Gender

Inclusion/Exclusion Criteria Form

- Participants with prior medical or laboratory training should be excluded.
- Participants who have prior experience with self-collection should be excluded.
- Participants who have previous SARS-CoV-2 testing should be excluded.

Subject ease of use survey

- After-Scenario Questionnaire (ASQ)

Other subject-reported data

- Survey for written comments
 - What, if any, steps did you have trouble completing?
 - Do you have suggestions for improving the collection instructions?
- Questions to evaluate comprehension of the IFU
 - Follow up by observer if necessary
- Subject-specific questions about not completed tasks and tasks completed with use errors or close during observation

Observer

- Observer Script
- Checklist based on tasks in the SARS-CoV-2 Specimen Collection Materials which documents the following outcomes with free fields for observational notes:
 - Completed
 - Completed with use errors, close calls
 - Did not complete

CONFIDENTIAL

May not be reproduced nor disseminated outside of Exact Sciences without permission

## 1. OBJECTIVES

### 1.1 Primary Objective

- 1.1.1 The primary objective is to determine the usability of the SARS-CoV-2 Specimen Collection Materials for at-home collection and mailing of sample to the testing laboratory.

### 1.2 Secondary Objectives

- 1.2.1 Evaluate perceived usability of the Instructions for Use (IFU).
- 1.2.2 Evaluate comprehension of IFU by the subject.
- 1.2.3 Identify problems that occur while following the IFU.
- 1.2.4 Evaluate root causes of problems that occur while following the IFU.
- 1.2.5 Develop strategies to mitigate problems occurring while following the IFU.

### 1.3 Exploratory Analyses

## 2. SCOPE

This Statistical Analysis Plan (SAP) pre-specifies the methodology for analyzing the primary, secondary, and exploratory objectives of the Usability Study of Home Collection and Mailing with SARS-CoV-2 Test Specimen Collection Materials, study Protocol 2020-06. This study is a prospective observational human factors usability study of approximately 30 subjects. The study design, methods and results will be described in a Clinical Study Report (CSR). The CSR will be attached to a regulatory filing with the United States Food and Drug Administration (FDA). The filing will support the Accelerated Emergency Use Authorization (EUA) (EUA 200367) for the at home self-collection of a nasal specimen and return to the testing laboratory for the Exact Sciences Laboratories (ESL) SARS-CoV-2 (N gene detection) Test

## 3. BACKGROUND

The Centers for Disease Control and Prevention (CDC) in the United States suggests laboratory testing to identify the SARS-CoV-2 virus that causes COVID-19. The FDA has given EUA for select Real-Time reverse transcription polymerase chain reaction (RT-PCR) Diagnostic Panels that detect ribonucleic acid (RNA) specific to SARS-CoV-2. This study will use the ESL SARS-CoV-2 (N gene detection) Test.

The ESL SARS-CoV-2 (N gene detection) Test provides a qualitative result based on detection of RNA. The test measures the presence of two regions of the RNA related to the SARS-CoV-2 nucleocapsid protein N gene (N1 and N2), which are specific for this virus. Both N1 and N2 RNA must be detected for a positive result and are indicative of active infection by the virus. A positive result does not rule out other infections. Detection of only one of the two viral RNAs results in an Inconclusive test. Negative results (Not detected) do not rule out infection and should be used in combination with clinical and epidemiological information for patient management decisions. The ESL SARS-CoV-2 (N gene detection) Test also measures RNA related to ribonuclease (RNase) P, which is a human protein and acts as an internal reference. The absence of the viral and human RNA would lead to an invalid test result.

# Statistical Analysis Plan: Usability Study of Home Collection and Mailing with SARS-CoV-2 Test Specimen Collection Materials (Protocol 2020-06)

**Doc. ID Number:**

**Revision Number:**  
1.0

**Effective Date:**

Page:  
4 of 35

SARS-CoV-2 N1	SARS-CoV-2 N2	Human RNase P	Report Result	Next Step
+	+	+/-	Positive	N/A
one +, one -		+/-	Inconclusive	Sample sent for alternative testing
-	-	+	Not Detected	N/A
-	-	-	Invalid	Specimen inadequate. Recollect if clinically indicated.

**Table 1:** Possible ESL SARS-CoV-2 (N gene detection) Test results based on RNA detected.

While the CDC provides guidelines for the collection of a wide range of upper and lower respiratory samples, the ESL SARS-CoV-2 (N gene detection) Test is for use with upper respiratory (nasal swab) samples from subjects receiving a clinically indicated COVID-19 Test.[1]

Emphasis has been placed on increasing overall testing availability, and the access to at home SARS-CoV-2 specimen collection (without healthcare worker supervision) is believed to improve the effectiveness of public health tools in preventing spread of the disease during this pandemic in the United States.

This study is a prospective observational human factors usability study. It will be complete when approximately 30 self-collected nasal swab samples have corresponding SARS-CoV-2 test results (positive, negative, inconclusive, or invalid). Subject participation is up to one day from enrollment to completion.

